### 5.1.3 Exploratory Endpoints

- 50% responder rate in total POS, SGS, and PGTCs; 50% responders are defined as subjects who have at least a 50% reduction in seizure frequency relative to baseline (in subjects with sufficient baseline seizure frequency data).
- 75% responder rate in total POS, SGS, and PGTCs; 75% responders are defined as subjects who have at least a 75% reduction in seizure frequency relative to baseline (in subjects with sufficient baseline seizure frequency data)
- Median percent change in total POS, SGS, and PGTCs frequency in the Titration and Maintenance Periods relative to baseline (in subjects with sufficient baseline seizure frequency data)
- Proportion of subjects with no/mild/clear cognitive impairment relative to baseline using the EpiTrack total score
- Change in subjective sleep quality at the end of the Maintenance Period relative to baseline using the PSQI
- Change in quality of life at the end of the Maintenance Period relative to baseline using the QOLIE-31
- Proportion of subjects with Depression relative to baseline using BDI-II scores.

## 5.2 Study Subjects

### 5.2.1 Definitions of Analysis Sets

The Safety Analysis Set (SAS) is the group of subjects who received at least 1 dose of study drug and had at least 1 postdose safety assessment.

The Full Analysis Set (FAS) is the group of subjects who received at least 1 dose of study drug and had at least 1 postdose seizure measurement.

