#### 9.4.5 Selection and Timing of Dose for Each Subject

Subjects will begin receiving perampanel 2 mg/day and be up-titrated in increments of 2 mg to a maximum dose of 12 mg, depending on the clinical response and tolerability in each subject. Subjects will start taking study drug at bedtime at Visit 2 (Week 0).

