#### **9.5.1.2      Efficacy Assessments**

Exposure data will be utilized to assess the primary endpoint. Secondary efficacy variables will be based on seizure frequency. Seizure frequency data will be collected in subject diaries by subjects or guardian/legally authorized representative during the study including the Titration Period and the Maintenance Period. Baseline seizure frequency data for up to 12 weeks before Visit 2 (Week 0) will be collected by subjects or guardian/legally authorized representative, retrospectively (for history prior to screening) and prospectively (during baseline). Subjects will be eligible for study enrollment after they have experienced the 2 unprovoked (or reflex) seizures occurring greater than 24 hours apart, or 1 unprovoked (or

reflex) seizure with EEG evidence of seizures, and will not need to complete the full 12-week diary to enter the Titration Period. (revised per Amendment 01) Seizure frequency data in subject diaries will be reviewed with the investigator(s) at Visit 2, 4, 5, 6, and 7. Seizure frequency from diary entries or principal investigator verification will be used to assess efficacy endpoints as appropriate. (revised per Amendment 01)

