#### **9.7.1.6.1 PRIMARY EFFICACY ANALYSIS**

The SAS will be used to summarize retention rate. The retention rate, defined as the proportion of patients remaining on perampanel treatment at 3, 6, 9, and 12 months after initiation of treatment, will be summarized.

The number and percentage of subjects remaining on treatment at each time point and 95% CIs will be summarized.

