## 5.4 Efficacy Analyses

This is a study without a control arm. Therefore, only descriptive statistics will be performed. The SAS will be used to summarize retention rate and the FAS will be used to summarize

seizure data.

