#### 5.4.1 Primary Efficacy Analyses

The retention rate, defined as the proportion of subjects remaining on perampanel treatment at 3, 6, 9, and 12 months after initiation of treatment, will be summarized. The number and percentage of subjects remaining on treatment at each time point will be summarized using SAS. Corresponding 95% CIs may also be presented if allowed by the data.

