#### 8.1.2 Treatment Duration for Efficacy Analyses

The date of first dose of the study drug is considered day 1 in the treatment duration. The first dose date is the study drug start date and the last dose date is study drug end date from the

study medication CRF page. The end of treatment (EOT) value is the last non-missing value while on-treatment.

The treatment duration for efficacy variables is defined as follows:

- For diary seizure data: The duration between the date of first dose and the last date of study drug in treatment duration (Titration Period and Maintenance Period), inclusive.
- For non-diary efficacy data: The duration between the date of first dose and 7 days after the last visit of schedule in treatment, inclusive.
- Data reported only during the treatment duration will be analysed.

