**Table 1: Mapping of Study Day Ranges to Week**

Period	Study Week	Study Day Range (Relative to First Dose of Study Drug)	Target Day
Screening	Baseline	Day $\leq 1^a$	1
Titration	Week 13	$2 \leq \text{Day} \leq 138$	92
Maintenance	Week 26	$139 \leq \text{Day} \leq 229$	183
Maintenance	Week 39	$230 \leq \text{Day} \leq 320$	274
Maintenance	Week 52	$321 \leq \text{Day} \leq 999^b$	365

- a: All assessments at Visit 2 were to be performed prior to first dose of study drug; results from these assessments will be regarded as Pretreatment values in the analyses.
- b: The last non-missing value measured in the treatment duration will be handled as the data of EOT of the Study. The Follow-up visit will not be included in this analysis visit.

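### The primary retention rate uses the Safety Analysis Set, so a dosed subject lost before any postdose safety assessment would leave the denominator instead of counting as not retained

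*SAP*

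**What the plan says.** SAP 5.1.1 and protocol 9.7.1.1.1 define the primary endpoint as the proportion still on perampanel at 3, 6, 9 and 12 months, counted from the start of treatment. Protocol 9.5.1.2 names the data: "Exposure data will be utilized to assess the primary endpoint". SAP 8.1.2 names the study medication CRF page as the source of the dates, in a sentence beginning "The first dose date is the study drug start date and the last dose date is study drug end date from the".

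Both documents use the Safety Analysis Set. SAP 5.4, which keeps the Full Analysis Set for seizure data, has a sentence beginning "The SAS will be used to summarize retention rate and the FAS will be used to summarize", and SAP 5.4.1 adds "The number and percentage of subjects remaining on treatment at each time point will be summarized using SAS". Protocol 9.7.1.6.1 agrees: "The SAS will be used to summarize retention rate". SAP 5.2.1 and protocol 9.7.1.2 define that set identically, as subjects who "received at least 1 dose of study drug and had at least 1 postdose safety assessment".

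On timing, protocol 9.4.5 has the first dose taken at bedtime on the day of Visit 2. Note a to the visit-window table in SAP 8.2.2 says "All assessments at Visit 2 were to be performed prior to first dose of study drug". In protocol Table 4, Week 2 is a dose change and not a visit. The first scheduled postdose contact that records adverse events is telephone Visit 3 at Week 4.

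**The concern.** The endpoint needs two facts for each subject: that treatment began, and whether it was still being taken at the time point. Neither requires a safety assessment. The second condition of the Safety Analysis Set depends on the subject staying in contact after the first dose, and staying in contact is itself related to staying on treatment.

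Nothing done at Visit 2 can meet the condition, because the dose comes afterwards. A subject who starts the drug and is lost within the first four weeks may have no postdose safety assessment. Protocol 9.3.3.2 classes anyone who took at least one dose but could not participate as a withdrawal, and it lists loss to follow-up among the reasons. In a retention analysis that subject is an early failure. Under the current rule the subject is left out of the calculation.

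The SAP handles its secondary endpoints differently. Section 5.4.2 counts early dropouts as not seizure-free and not converted. Section 5.4.1 has no matching rule for the primary endpoint. SAP Section 7 says enrollment ended early and that there are too few subjects for 95% confidence intervals. The rate may therefore be reported as a bare point estimate from a small sample, where each subject carries more weight.

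**Working it through.** **Figures available.** The plan gives no expected retention rate, precision target or final sample size, so there is no stated figure to reproduce. The planned N is about 125 (SAP Section 4). The final N is lower but not given (SAP Section 7), and 40 is used here as an assumption. Retention is assumed to be 70%, with a range of 50% to 90%. The number excluded, k, is unknown.

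**Formula.** Let N be the subjects with a recorded first dose, r those retained, and k the dosed subjects outside the Safety Analysis Set, none of them retained.

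- Rate under the plan: p = r/(N − k)
- Rate on all dosed subjects: r/N
- Difference: r/(N − k) − r/N = rk/[N(N − k)] = p × k/N

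The difference cannot be negative, and it is zero when k = 0.

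**Results for k = 1, in percentage points.**

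| N | p = 50% | p = 70% | p = 90% | 95% half-width at 70% |
|---|---|---|---|---|
| 125 (planned) | 0.40 | 0.56 | 0.72 | 8.0 |
| 40 (assumed) | 1.25 | 1.75 | 2.25 | 14.2 |

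For example, 0.70 × 1/125 = 0.56 points and 0.70 × 1/40 = 1.75 points. The half-widths are 1.96 × √(0.21/125) = 8.0 points and 1.96 × √(0.21/40) = 14.2 points. At fixed p the shift is proportional to k.

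**Check in whole subjects, k = 1.**

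- 87/124 = 70.16% against 87/125 = 69.60%, a difference of 0.56 points.
- 27/39 = 69.23% against 27/40 = 67.50%, a difference of 1.73 points.

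**Are the excluded subjects non-retained?** The direction depends on this. Drug is dispensed at Visit 2 and not again until Week 13 (protocol 9.4.1). That visit also records adverse events and vital signs (Table 4). A subject with no postdose safety assessment at all could hardly be documented as on drug at 3 months or later. If such a subject were somehow counted as retained, exclusion would lower the rate: 88/125 = 70.4% would become 87/124 = 70.2%. The visit schedule makes that implausible.

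**The case against.** The strongest objection is that the affected group may be empty. Protocol 9.5.1.6 lists discontinuation from treatment among the safety assessments, so a disposition record might itself satisfy the condition. Withdrawn subjects are to have a Follow-Up Visit (9.1.4), and those who stop attending are pursued by mail, phone or other means (9.5.5). Confirming a bedtime dose normally needs a later contact, and planned contacts record adverse events. All of this stands. It makes k small or zero, but it does not guarantee zero, and neither document says how a dosed subject without a qualifying assessment is classified.

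The protocol and SAP also agree on the set, and the disposition table will show the size of each set. That is correct. This is an analysis choice and not a contradiction. Reporting the set sizes would reveal an exclusion but would not correct the rate.

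A reader might infer that using this set can only raise the rate, or that the reported rate will be inflated. The documents do not support either as a certainty. The first requires the excluded subjects to be non-retained, and the second requires at least one to exist.

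A reader might also want to count as not retained anyone without recorded dosing at the time point. That goes too far. Visit 7 is Day 365 with a window of ±7 days, drug is returned there, and doses are taken at bedtime. An on-schedule completer may take the last study dose on Day 364. One seen seven days early (Day 358) may take it on Day 357. Such a rule could label completers as failures even with k = 0. At an interim cut it would do the same to subjects who have not yet reached the time point.

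**Conclusion.** The point holds, as a minor one. The denominator of the primary endpoint carries a condition that the endpoint does not use and that an early loss can fail. Where such a loss occurs, the retention rate rises at all four time points. The mechanism follows from the text, but the size cannot be known from it. Each such subject would add about 0.6 points at N = 125 and about 1.8 points at an assumed N = 40, at an assumed 70% retention. This is small beside sampling error, and there is no effect if no dosed subject is excluded. No hypothesis is tested, so only the reported estimate is affected. The direction rests on the excluded subjects being non-retained, which the dispensing and visit schedule supports for the final analysis.

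**What to change.** In SAP 5.4.1, define the retention denominator as all subjects with at least one recorded dose, identified by a study drug start date on the study medication CRF page. State that in the final analysis a dosed subject with no postdose contact counts as not retained at every time point. Limit the rule to those subjects.

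If this set and the Safety Analysis Set differ, report the protocol-specified rate alongside and state how many dosed subjects fall outside the Safety Analysis Set. Record the change in SAP Section 7, which at present lists no change to the retention denominator. Keep the Safety Analysis Set for the safety tables.

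The work is a short addition to 5.4.1 and one entry in Section 7, with no new data. The costs are a documented departure from protocol 9.7.1.6.1 and a retention figure that stays the same or falls slightly. There is also one new risk. The documents do not say how a start date is confirmed, so the wider set could include a subject whose start date was recorded but whose first dose was never confirmed. Subjects with no recorded start date remain outside both sets.

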**Table 4 Schedule of Procedures/Assessments in Study E2007-G000-410 (revised per Amendment 01)**

Period	Screening a	Titration b (Wk 0 to Wk 12)				Maintenance b				Early Discontinuation	Follow- Up b,c	Unscheduled d
		Wk -6 to Wk 0	Wk 0	Wk 2 e	Wk 4	Biweekly f,g	Wk 13	Wk 26	Wk 39			
Study Week(s)												
Study Day		1	15	29		92	183	274	365			
Visit Number	1	2		3		4	5	6	7		8	
Procedure/ Assessment												
Return and review subject diary		X				X	X	X	X	X		

AED = antiepileptic drug, BDI-II = Beck Depression Inventory II, eCRF = electronic Case Report Form, C-SSRS = Columbia-Suicide Severity Rating Scale, PSQI = Pittsburgh Sleep Quality Index, QOLIE-31 = Quality of Life in Epilepsy Inventory-31, Wk = week.

a: Up to 12 weeks of baseline seizure frequency to be determined at screening; any screening assessments may be repeated during the Screening Period, at the discretion of the investigator.

b: Visit to be done within ±7 days of the schedule. Subjects may continue to receive commercial perampanel during the Follow-Up Period. (revised per Amendment 01)

c: To be completed by subjects who are withdrawn from the study for any reason after Visit 2 (Week 0) and before Visit 6 (Week 39). (revised per Amendment 01)

d: At the unscheduled visit, only the assessments that the investigator(s) judged necessary based on the subject's condition will be performed

e: At the end of Week 2, the perampanel dose increases from 2 to 4 mg; this is not a visit.

f: Telephone Visit; all dose adjustments and rationale for the adjustments, as well as adverse events will be recorded on the eCRF.

g: Follow-up telephone calls to Visit 3 may occur biweekly, or at a frequency of the investigator's discretion. All dose adjustments and rationale for adjustments, as well as adverse events will be recorded in the eCRF.

h: Informed consent/assent may be obtained prior to study start; it must be obtained prior to any study related procedures.

i: All pertinent medical and surgical history within 5 years before Visit 1 (Week 0).

j: Prior and concomitant medication(s) within 24 weeks (and as long as available for AED[s]) before Visit 2 (Week 0).

k: Subjects 6 years and older. EpiTrack Junior will be administered for subjects aged ≥6 to 16 years old. (revised per Amendment 01)

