#### **9.7.1.6.2 SECONDARY EFFICACY ANALYSES**

The FAS will be used to summarize seizure data.

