#### 5.4.2 Secondary Efficacy Analyses

The FAS will be used to summarize seizure freedom data and conversion data of perampanel as a 1st adjunctive therapy converted to perampanel monotherapy. The number and percentage of subjects who achieved seizure-free status or who converted to perampanel monotherapy will be summarized. 95% CIs may also be calculated if allowed by the data.

The seizure-free status at 3-month in Maintenance Period, at 6-month in Maintenance Period, and during the entire Maintenance Period will only be counted for subjects who complete the respective period. A subject who dropped out early relative to the respective period would be counted as 'No' for seizure-free status in that period.

A subject is considered converted to perampanel monotherapy during Maintenance Period if the subject had a scheduled visit in Maintenance Period and was not taking any concomitant AED at any time during the scheduled visit. A subject who dropped out early before the conversion would be counted as 'No' for conversion status.

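### Seizure freedom and conversion are computed on the FAS, so a titration dropout with no postdose seizure measurement leaves the denominator instead of being counted as a 'No'

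*SAP*

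**What the plan says.** **The analysis set.** SAP 5.2.1 defines the FAS as subjects who "received at least 1 dose of study drug and had at least 1 postdose seizure measurement". Protocol 9.7.1.2 defines it the same way.

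**Where it is used.** SAP 5.4.2 states: "The FAS will be used to summarize seizure freedom data and conversion data of perampanel as a 1st adjunctive therapy converted to perampanel monotherapy". Protocol 9.7.1.6.2 says only: "The FAS will be used to summarize seizure data". It names no set for conversion.

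**The dropout rule.** SAP 5.4.2 continues: "A subject who dropped out early relative to the respective period would be counted as" 'No' for seizure freedom in that period. It has a parallel rule for subjects who leave before converting. The sentence just before says that seizure-free status counts only for those who finish the period in question.

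**How conversion is judged.** The subject must have had a scheduled visit in the Maintenance Period and "was not taking any concomitant AED at any time during the scheduled visit".

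**When seizure data are collected.** Protocol 9.5.1.2: "Seizure frequency data in subject diaries will be reviewed with the investigator(s) at Visit 2, 4, 5, 6, and 7". In Table 4, the row "Return and review subject diary" is marked at Weeks 0, 13, 26, 39 and 52 and at early discontinuation. It is not marked at the Week 4 telephone visit or the biweekly calls. The footnote for telephone contacts reads: "Telephone Visit; all dose adjustments and rationale for the adjustments, as well as adverse events will be recorded on the eCRF".

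**The concern.** The SAP clearly means an early dropout to be a failure for both endpoints. The rule works only on subjects already in the FAS, and entry to the FAS depends on having a seizure measurement after dosing. Titration lasts up to 13 weeks, and no on-treatment diary review is scheduled before Week 13 unless the subject attends an early discontinuation visit. A subject lost after the Week 4 call can therefore have adverse event data but no seizure measurement. That subject is a failure under the dropout rule, yet is absent from the denominator.

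The study is single-arm and descriptive, so the rate is itself the result. SAP Section 7 adds that enrolment stopped early and that the sample is too small for 95% confidence intervals, so these point estimates may be reported alone.

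**Working it through.** The plan has no figure to reproduce. It gives no expected seizure-free, conversion or dropout rate, and the target of about 125 subjects rests on no precision calculation. The check is a reading of the rules followed by simple arithmetic.

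**Step 1: which subjects are affected?** A dosed subject who stops in titration, does not attend the early discontinuation visit, and supplies no diary or other seizure information. This subject fails the FAS condition.

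**Step 2: what would this subject's outcome be?** Both endpoints are judged in the Maintenance Period (SAP 5.4.2). A titration dropout completes no part of it and has no scheduled visit in it, so is 'No' on both.

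**Step 3: direction and size.** Let N be the number dosed, x the number with a 'Yes', m the number of excluded failures, and f = m/N.

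- Rate on all dosed subjects: x/N
- Rate on the FAS: x/(N - m) = (x/N) × 1/(1 - f)

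The numerator does not change and the denominator shrinks, so the rate can only rise. The relative inflation depends on f and not on N.

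**Step 4: numbers.** All inputs are assumptions. For a true seizure-free rate of 40%:

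| f | FAS rate | Shift (points) |
|---|---|---|
| 0 | 40.0% | 0 |
| 1% | 0.40/0.99 = 40.4% | +0.4 |
| 2% | 0.40/0.98 = 40.8% | +0.8 |
| 5% | 0.40/0.95 = 42.1% | +2.1 |

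For conversion, assume 40 dosed first-adjunctive subjects and 12 converters: 12/40 = 30.0%. If 2 titration dropouts fall outside the FAS, the reported rate is 12/38 = 31.6%.

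The SAP also splits seizure-related results by seizure type, sex and age group (5.3.4), where one subject weighs more. In an assumed subgroup of 10 with 4 seizure-free, losing one dropout changes 4/10 = 40.0% to 4/9 = 44.4%.

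**Step 5: does conversion need the FAS?** No. It is decided from concomitant AED use at a scheduled visit, and Table 4 collects concomitant AEDs at every site visit. The seizure-measurement condition adds nothing to the assessment. It comes from the SAP, not the protocol.

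**The case against.** **Few subjects may be affected.** Protocol 9.5.5 asks everyone who discontinues to complete the early discontinuation procedures, which include diary return, and has non-returners traced. The synopsis accepts information gathered retrospectively, and 9.5.1.2 accepts verification by the principal investigator. Telephone contacts weigh response before any dose increase, so some seizure information may exist from Week 4. Neither document defines a postdose seizure measurement, so such sources might count. This stands: f may be small or zero. A definition would help fix FAS membership, but it would not bring in a dropout who gives no information, and it would leave conversion tied to an irrelevant condition.

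**The set follows the protocol.** For seizure freedom this is correct. A reader might infer that the SAP contradicts itself. It does not: a dropout rule applied inside a declared set is limited by that set. The weakness is that the rule reaches fewer dropouts than it appears to.

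**The disposition table will show the numbers in each set.** This also stands, but it does not correct the rates, and the number dosed is not among the listed items.

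**The completers sentence.** A reader might take the sentence before the dropout rule to remove every early dropout from the denominator, which would be a much larger effect. The next sentence scores those same dropouts as 'No', so the coherent reading is that completion limits who can be a 'Yes'. The SAP should say so.

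**Conclusion.** The point holds as a cheap improvement of small and unknown size. Under the definitions as written, a titration dropout with no seizure information is lost from both rates, and each loss moves the rate upward. The shift is 0.4 to 2.1 points on an assumed true 40%, for assumed f between 1% and 5%, and nothing if f is zero. The case is strongest for conversion.

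Two stronger readings are not supported:

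- **That the primary retention rate is inflated in the same way.** Retention uses the Safety Analysis Set, which requires a postdose safety assessment, not a seizure measurement. Adverse events are scheduled at the telephone contacts, protocol 9.5.1.6 lists discontinuation from treatment among the safety assessments, and non-returners are traced. The documents give no reason to change that set.
- **That the error could go either way because converters, or subjects still on drug, might lack seizure data.** Every scheduled Maintenance visit includes diary return and review, and investigator verification is accepted, so such subjects should be close to non-existent.

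**What to change.** In SAP 5.4.2:

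1. For seizure freedom, use all subjects with at least one dose, within each seizure type, as the denominator. For conversion, use all dosed first-adjunctive subjects.
2. Count every early dropout as 'No', with or without a postdose seizure measurement.
3. State that the sentence on completing the period limits who can be a 'Yes' and does not define the denominator.
4. Show the FAS rates alongside, and report the number dosed and the number of dosed subjects outside the FAS.
5. Declare the change in SAP Section 7, noting that the protocol assigns the FAS to seizure data and names no set for conversion.

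No new data are needed: dosing dates, disposition, seizure type and concomitant AED records are already collected. The cost is a declared departure from the protocol's set for seizure data, one extra row of rates, and rates that may fall slightly.
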